- To describe the adverse events encountered, their severity according to ASGE standards and their management.
- To describe the time elapsed between the procedure and the initial oral intake.
- To describe the evolution of the oral intake during the first month after the procedure
- To assess the impact of the operators experience on procedure times, adverse events and technical issues.
- To assess the impact of the procedure on the quality of life of the participating patients.

4. Design

Prospective, multicenter case-series

5. Methods

Study population

All consecutive patients over 18 years of age submitted to any of the participating center's endoscopy units to receive a nasobiliary drain assisted EUS-GE for unresectable malignant GOO are eligible to participate in this study.

Inclusion and exclusion criteria

Inclusion criteria:

- Unresectable malignant gastric outlet obstruction
- Scheduled placement of a nasobiliary drain assisted EUS-GE
- Age >18 years.

Exclusion criteria:

- Previous gastroduodenal surgery
- Previous endoscopic or surgical treatment for gastric outlet obstruction
- Simultaneous malignant biliary obstruction requiring endoscopic treatment
- Unable to understand the questionnaires
- Distal bowel obstruction
- Ascites grade 2 or superior
- Uncorrectable coagulation disorders (INR>1,5) or severe thrombocytopenia (<50000 platelets/mm3).

Definitions of the outcomes employed to assess primary and secondary variables

1. Technical success: Dichotomous variable. Defined as a correct placement of the LAMS, with one flange inside the gastric cavity and the other one in the small bowel. It should be confirmed endoscopically or fluoroscopically

2. Clinical success: Dichotomous variable. Defined as a GOOSS ≥ 2 . It will be assessed at days +7 and +30.
- 3.
4. Recurrent GOO: Dichotomous variable. In patients achieving clinical success in day +7, recurrent GOO is defined as the development of nausea and vomiting and/or a GOOSS < 2 .
5. Persistent GOO: Dichotomous variable. Continuing nausea, vomiting, and inability to tolerate PO intake up to or occurring within 2 weeks after the procedure.
6. Major complications: life-threatening or severe complications requiring treatment and/or hospitalization (The adverse event severity will be graded according to the ASGE lexicon).
 - a. Early major complications: complications occurring within 7 days after the intervention.

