 - b. Late major complications: complications occurring 7 days or later after the intervention.
7. Minor complications: not life-threatening or moderate or severe complications that do not require hospital admission.
8. Reintervention: Dichotomous variable. Any procedure (endoscopic, radiologic or surgical aiming at treating a recurrent GOO, persistent GOO or any procedure related adverse event).
9. Gastric outlet obstruction score system: Presents the following categories 0 (*nil per os*), 1(liquids), 2(soft diet), 3 (full diet or low residue diet).
10. Target bowel loop diameter (mm): Diameter measured with the EUS of the dilated bowel loop. It should be measured just before placing the stent.

11. Total volume infused (ml): Volume of saline, methilene blue solution or radiopaque contrast solution instiled to dilate the target bowel loop (each one will be individually measured).

12. Balloon dilation: Dichotomous variable. At discretion of the endoscopist, after deploying the stent, it might be dilated with a controlled radial expansion balloon dilator.

Intervention

At inclusion

Informed consent will be obtained. A clinical interview and a physical examination will be performed. The European Organization for Research and Treatment of Cancer QoL Questionnaire Core 30 (EORTC-QLQ-C30), which includes 30 items covering a global health status scale, five functional scales and ten symptom scales will be assessed in a telephone interview.

Endoscopic procedure

All procedures will be performed under sedation. An assistant endoscopist or research nurse will retrieve all data regarding the procedure. Firstly, an upper digestive endoscopy is performed with a conventional gastroscope. A guidewire is passed through the malignant lesion causing the gastric outlet obstruction. Once the guidewire is located in the distal duodenum/proximal jejunum, a nasobiliary drain (Nasal Biliary Drainage Sets, Cook medical, Indiana) is advanced over the guidewire until its distal end is placed in the distal duodenum/jejunum. At this point the gastroscope is substituted by a therapeutic echoendoscope. With the echoendoscope in place, the target bowel loop is filled with saline combined with methilene blue and radiopaque contrast. The echoendoscope is used to identify the target bowel loop. After

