identifying the target, a lumen apposing metal stent (Axios, Boston Scientific, Massachusetts) is deployed across the gastric and bowel using its electrocautery enhanced deployment device.

Post procedure

Oral liquid intake can be restarted 4h after the procedure in patients presenting no signs or symptoms suggesting any adverse event. Patients with an adequate tolerance might be discharged.

Follow-up

Clinical telephone interviews by an experienced research nurse will be held via telephone calls 1 day, 7 days and 30 days after the procedure. Oral intake and adverse events will be assessed every visit. Thirty days after the procedure a second evaluation of the EORTC-QLQ-C30 will be performed.

Sample size

Although EUS-GE is a rather infrequent procedure, we aim at including at least 5-10 procedures/endoscopist, in order to present each operator's *modus operandi*. Thus, recruitment will be active until a minimum of 5 procedures/endoscopist is reached or until a total sample size of 50 patients is reached, with at least 4 endoscopists including >5 procedures). To assess the secondary endpoint of the quality of life, previously published papers assessing QoL in patients with unresectable malignant GOO using the EORTC-QLQ-C30 reported mean global health status scores of 36.6 (SD: 20.1) and 45 (SD: 20.3) before treatment. To detect at least a 14-points change

with a 5% alfa risk and an 80% power, 33 subjects were estimated to be needed. Assuming a 20% of losses, 40 patients were required.

Adverse events monitoring

Adverse events (AE) are defined as any event preventing from completing the procedure, causing or lengthening a hospital admission or conditioning further interventions or unscheduled hospital or out-patient clinic visits. According to the time of diagnosis, they are classified as intraprocedure (diagnosed in the endoscopy unit during or immediately after the procedure), postprocedure (diagnosed in the 7 days following the procedure) or delayed (diagnosed beyond the first 7 days after the procedure). Causal relationship will be categorized into definitive (clearly related), probable (probably related), possible (might be related) or unlikely (there are other more likely causes). Severity will be assessed according to the ASGE recommendations

Consequence	Severity			
	Mild	Moderate	Severe	Fatal
Stop (or not even starting) a procedure	x			
Post-procedure out-patient visit	x			
Unplanned respiratory support during the procedure		x		

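### Outcome definitions 6 and 7 do not put every complication in exactly one class, and they disagree with the adverse-event section at day 7

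*Combined protocol and SAP*

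**What the plan says.** Section 5 (Methods) lists the outcome definitions. Item 6 defines major complications as "life-threatening or severe complications requiring treatment and/or hospitalization" and adds that severity is graded by the ASGE lexicon. It divides them in time:

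- Item 6a: "Early major complications: complications occurring within 7 days after the intervention".
- Item 6b: "Late major complications: complications occurring 7 days or later after the intervention".

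Item 7 defines minor complications as "not life-threatening or moderate or severe complications that do not require hospital admission".

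Later in Section 5, Adverse events monitoring sets out a second system, which sorts events by when they were diagnosed. The first class is "intraprocedure (diagnosed in the endoscopy unit during or immediately after the procedure"). For everything found after that stage, the section gives two further classes: "postprocedure (diagnosed in the 7 days following the procedure) or delayed (diagnosed beyond the first 7 days after the procedure"). A table then grades each event mild, moderate, severe or fatal by its consequence. Unplanned admission is mild up to 3 nights, moderate for 4-10 nights and severe from 11 nights. The other severe rows are two or more nights in intensive care, surgery and permanent disability.

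Follow-up is by "telephone calls 1 day, 7 days and 30 days after the procedure". On what these calls cover, the plan says: "Oral intake and adverse events will be assessed every visit". Nothing maps major/minor to the table grades or early/late to the timing classes, and nothing says which system governs reporting.

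**The concern.** A classification used for counting should give each event one label, and two classifications of the same events should agree where they share a cut-point. Items 6 and 7 appear to fail on both counts.

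They stand under a heading that makes them the definitions for the primary and secondary variables, so a reader would expect the report to use them. Followed as written, an event on day 7 could be counted twice, or be late in one table and not delayed in another. Some events could have no major/minor class, and others could have two. Centers or analysts reading the text differently would then produce different counts from the same data.

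**Working it through.** There is no planned figure to reproduce and no formula applies. The check sets the definitions side by side.

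**Timing.** Inputs are items 6a and 6b and the timing classes in Adverse events monitoring. The plan counts in days: calls on days 1, 7 and 30, and clinical success at days +7 and +30. Take an event that occurs and is diagnosed on the same day.

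| Day | Items 6a/6b, 6a including day 7 | Items 6a/6b, 6a read as under 7 days | Adverse-event section |
|---|---|---|---|
| 6 | early | early | postprocedure |
| 7 | early and late | late | postprocedure |
| 8 | late | late | delayed |

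Days 6 and 8 agree throughout. On the ordinary reading of 6a, day 7 carries two labels. On the stricter reading the overlap goes, but day 7 is then late under 6b and not delayed in the adverse-event section.

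The time anchors differ as well. An event that begins before the cut and is diagnosed after it is early by occurrence but delayed by diagnosis. The adverse-event section also has a small overlap of its own: an event diagnosed in the unit immediately after the procedure also lies in the 7 days that follow it.

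**Severity.** Inputs are items 6 and 7 and the severity table. Take events that are treated and not life-threatening, with severe in item 6 meaning the table grade. Item 7 can be read in several ways:

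- A: the listed types of event, all without admission.
- B: the opening negative governs the whole list, so minor means mild without admission.
- C: any event that is not life-threatening is minor, as is a moderate or severe one without admission.
- D: admission separates the classes. Any hospitalized event is major, as is any severe treated event; minor means not life-threatening and not admitted.

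| Event | A | B | C | D |
|---|---|---|---|---|
| Mild, not admitted | minor | minor | minor | minor |
| Mild, admitted | neither | neither | minor | major |
| Moderate, not admitted | minor | neither | minor | minor |
| Moderate, admitted | neither | neither | minor | major |
| Severe, not admitted | both | major | both | both |
| Severe, admitted | major | major | both | major |

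Every column has at least one event type in neither class or in both. Mixing the readings does not help. For example, if any admission is major (D) and item 7 is read as in C, a mild admitted event becomes both.

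The gap under A and B touches ordinary events, because causing or lengthening an admission is one of the plan's own criteria for an adverse event. The overlap that remains under D is narrow: two of the four severe rows are themselves admissions, which leaves surgery and permanent disability.

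**The case against.** Four arguments can be made for the plan.

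- **Elapsed time.** If events were timed exactly, all the cuts would fall at 7 x 24 hours and the conflict would shrink to that instant. This is correct. But the plan schedules and assesses in days, and nothing says events are timed to the hour. The difference between occurrence and diagnosis would remain in any case.
- **Purpose.** Reading D is a sensible account of what was probably meant, and under it no admitted event is lost. This also stands. A reader might infer that the definitions necessarily drop admitted patients; they do so only on readings A and B. Even so, D is not the literal text, and it leaves severe events without admission in both classes.
- **The ASGE grades do the work.** The secondary aim asks for severity by ASGE standards, item 6 itself refers to the ASGE lexicon, and neither the aims nor the statistical section calls for major/minor or early/late tables. This limits the consequence. It does not remove the inconsistency, because items 6 and 7 are listed as outcome definitions and nothing subordinates them.
- **Choice of anchor.** Dating by diagnosis rather than occurrence is a preference, and the documents do not show that either is right. This is so; what is needed is a single anchor.

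A reader might also infer from the calls at days 7 and 30 that the two systems could date a major event weeks apart. The documents do not support that. The calls are central research follow-up, each center runs its own local follow-up, and a major complication would normally be diagnosed when it is treated or admitted. The call schedule does not show that events cluster on day 7 either.

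**Conclusion.** The definitions are wrong as written, and the point is minor. Counted in days, items 6a and 6b conflict with each other or with the adverse-event section at day 7, and the time anchors differ. No reading of items 6 and 7 tried here gives a split that is both exclusive and exhaustive.

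The conclusion rests on counting in days and on taking severe in item 6 as the table grade. The number of events affected cannot be derived, because the documents give no event frequencies by grade, admission and day; the tables above show event types, not how often they occur.

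The effect is confined to descriptive early/late and major/minor counts. A reader might infer that safety reporting as a whole is compromised. It is not: the ASGE-graded severity aim and the centers' duty to report events both use the table grades. The primary aim and the sample size do not depend on items 6 and 7.

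**What to change.** Use one classification for reporting. Drop the major/minor and early/late labels in items 6 and 7. Report the table grades (mild, moderate, severe, fatal) by the timing classes of the adverse-event section, dated by diagnosis:

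- intraprocedure: diagnosed in the endoscopy unit, and counted only there;
- postprocedure: from the end of that period through day 7;
- delayed: after day 7.

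If the sponsor keeps major/minor and early/late, items 6 and 7 must be reconciled with the adverse-event section so that every event falls in exactly one class, with one time anchor and one cut at day 7. Where the major/minor boundary lies is for the sponsor to decide.

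The cost is rewording: the preferred option uses grades and timing classes already in the plan. The drawback is less direct comparison with series that report major and minor complications.

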The first endoscopic approach to achieve a functional gastrojejunostomy was through natural orifice transluminal endoscopic surgery (NOTES), where the peritoneal cavity is reached through the stomach. Once in the peritoneal cavity, a jejunal loop is clasped with a grasper and retrieved into the gastric cavity, suturing both hollow structures (5). Although prospective, proof of concept animal studies have shown its feasibility (6,7) and successful procedures in humans have been performed (8), it is a very demanding procedure even in highly skilled endoscopists. Endoscopic ultrasound guided gastroenterostomy (EUS-GE) is currently the preferred method to achieve an endoscopic gastric bypass in malignant GOO. An echoendoscope is used to identify the target bowel loop from the gastric cavity. To ease the identification of the target, different fluid solutions are injected into the bowel to distend it. Various methods have been proposed to reach this distention. In the endoscopy units taking part in the present study, the nasobiliary drain assisted EUS-GE is used, where a nasobiliary drain is advanced through the malignant stricture into the distal duodenum or the jejunum, and, once in place, liquids are pumped into the target bowel loop. Once the target bowel loop is identified, a lumen apposing metal stent (LAMS) is placed across both organs. After demonstrating its feasibility in animal studies (9,10), it has been extensively used in patients (11).

Available results of EUS-GE

Self-expandable metal stents (SEMS) achieve technical success in 97% of patients, with 87% achieving technical success, while a relevant proportion of patients present recurrent GOO, which presents approximately 3 months after deployment (12). A recent multicenter retrospective study comparing SEMS and EUS-GE observed similar proportions of technical and clinical success rates, while EUS-GE presented

lower rates of recurrent GOO and reintervention (13). Due to the low number of centers performing this procedure, the nasobiliary drain assisted EUS-GE has not yet been standardized, with significant differences among operators.

2. Objectives

Primary aim

- To describe different variants in the nasobiliary drain assisted EUS-GE technique, offering a detailed step by step description of the procedure performance by different endoscopists

Secondary aims

- To describe the proportions of technical and clinical success.

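### The rule for closing recruitment does not secure the 40 patients stated for 80% power on quality of life; the gap matters mainly with 4 or 5 endoscopists

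*Combined protocol and SAP*

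**What the plan says.** Under 5. Methods, Sample size, the plan sets its recruitment goal by operator: "we aim at including at least 5-10 procedures/endoscopist". It then gives two closing conditions joined by *or*: "recruitment will be active until a minimum of 5 procedures/endoscopist is reached or until a total sample size of 50 patients is reached". A qualifier follows, "with at least 4 endoscopists including >5 procedures". Section 8 (Timeframe, second year) repeats both conditions and the qualifier. The number of participating endoscopists is not given anywhere.

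The Sample size section then turns to quality of life. From published baseline SDs of 20.1 and 20.3 on the EORTC QLQ-C30 global health score and a 14-point change, it states: "with a 5% alfa risk and an 80% power, 33 subjects were estimated to be needed". It continues: "Assuming a 20% of losses, 40 patients were required". No sentence links this 40 to closure of recruitment.

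The primary aim is descriptive ("To describe different variants in the nasobiliary drain assisted EUS-GE technique"), and the design is a case series. Quality of life is one of six secondary aims: "To assess the impact of the procedure on the quality of life of the participating patients". It is the only analysis with a power statement.

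**The concern.** The 50-patient condition lies above 40 and leaves no gap. The per-endoscopist condition can end recruitment by itself, and its smallest total depends only on how many endoscopists take part. If that number is small, the study can close in full compliance with the rule without the patients that the plan says it required for quality of life.

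At stake is the accuracy of the one power claim in the plan. It is stated without conditions, but it holds only if enrolment happens to reach about 40. A reader cannot tell whether 40 is a condition for closing or a target.

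Two wording problems make the closing point harder to fix. The threshold is a minimum of 5 in one clause and more than 5 in the other. It is also unclear whether the 4-endoscopist qualifier applies to the 50-patient condition only or to both.

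**Working it through.** **Inputs from the Sample size section.** Alpha 5% (taken as two-sided; one-sided would give 26, not 33), power 80%, change 14 points, SD 20.1 and 20.3, losses 20%. Not given, hence assumed: the number of endoscopists k, their relative volumes, and the before-after correlation r.

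**1. The plan's own figure.** n = 2 × (1.96 + 0.8416)² × SD² / 14² gives 32.4, 32.7 and 33.0 for SD 20.1, 20.2 and 20.3. This reproduces 33. The formula equals a paired comparison with r = 0, since the SD of change is then 20.2 × √2 = 28.6.

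**2. Loss adjustment.** 33 × 1.2 = 39.6, which gives the stated 40. But 40 × 0.8 = 32 pairs. To keep 33 pairs, 33 / 0.8 = 41.25, so 42 must be enrolled.

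**3. Smallest total at closure.** If the qualifier governs only the 50-patient condition, the floor is 5k. If it governs both, the floor is 4 × 6 + 5(k − 4).

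| k | Qualifier on 50-patient condition only | Qualifier on both |
|---|---|---|
| 4 | 20 | 24 |
| 5 | 25 | 29 |
| 6 | 30 | 34 |
| 7 | 35 | 39 |
| 8 | 40 | 44 |

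On either reading the floor is below 40 for k of 7 or fewer.

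**4. How often closure falls below 40.** Each patient is allocated at random to an endoscopist at fixed relative volumes. Recruitment closes at the earlier of (a) every endoscopist at 5, and (b) at least 50 patients with four endoscopists at 6 or more.

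| k | Equal volumes | Uneven volumes |
|---|---|---|
| 4 | 92% | 75% (2:1:1:1), 43% (3:2:1:1), 27% (4:2:1:1) |
| 5 | 60% | 35% (2:1:1:1:1), 26% (2:2:1:1:1), 12% (3:2:1:1:1) |
| 6 | 17% | 4% (2:2:1:1:1:1), 2% (3:2:2:1:1:1) |
| 7 | about 1% | not run |
| 8 | 0% | not run |

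If the qualifier governs both conditions, equal volumes give 80%, 55%, 14% and under 1% for k = 4 to 7. The floor itself is rare: with equal volumes and the qualifier on the 50-patient condition only, about 1% of runs with 4 endoscopists, and about 0.2% or less with 5 to 7.

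**5. Power and detectable change by size.** Pairs m = 80% of enrolment; SD of change = 20.2 × √(2(1 − r)). Power = Φ(14√m / SD of change − 1.96). Detectable change at 80% power = 2.8016 × 28.6 / √m at r = 0.

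| Enrolled | Pairs | Power, r = 0 | r = 0.3 | r = 0.5 | Detectable change, r = 0 |
|---|---|---|---|---|---|
| 20 | 16 | 50% | 65% | 79% | 20.0 |
| 25 | 20 | 59% | 75% | 87% | 17.9 |
| 30 | 24 | 67% | 82% | 92% | 16.3 |
| 35 | 28 | 74% | 87% | 96% | 15.1 |
| 40 | 32 | 79% | 91% | 98% | 14.1 |

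**6. Power averaged over simulated closing sizes, r = 0.** With 4 endoscopists: 65% equal, 71-84% uneven. With 5: 76% equal, 80-85% uneven. With 6 and 7 equal: 83% and 86%. At r = 0.3, equal volumes give 79% with 4 and 89% with 5; at r = 0.5, 90% and 96%.

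**The case against.** The strongest reply is that little power is lost in most scenarios. By the plan's own formula, a study of exactly 40 has 79% power after losses. Against that, the existing rule averages 3 points less with 5 equal-volume endoscopists, and as much or more with 5 of uneven volume or with 6 or more. Even with 4 endoscopists, strongly uneven volumes bring the average to about 80-84%. The loss also depends on r = 0, whereas the same patients are measured before and after, so some positive correlation is plausible. All of this stands, and it limits the size of the point.

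Two further replies carry less weight. The rule serves the descriptive primary aim, which is a reason to keep it but not to leave an unconditional power statement beside it. And *or* might have been meant as whichever comes later, in which case the total could not fall below 50; the text does not say so, and if that was the intention it needs to be written.

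A reader might infer that the study is under-powered, or that it will close near 20 patients with about 50% power. The documents do not support either. They give neither the number of endoscopists nor the correlation, and the floor is seldom reached.

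**Conclusion.** The closing rule does not secure the stated 40 patients, and therefore does not secure the stated 80% power, if 7 or fewer endoscopists take part. That follows from the text and from multiplication, and it does not depend on r.

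The practical risk is concentrated at 4 or 5 endoscopists. Average power falls clearly below the plan's figure only with 4 of equal or mildly uneven volume, and slightly with 5 of similar volume, in each case at low correlation. The probabilities rest on random accrual at fixed volumes and on closure at whichever condition is met first. What is shown is an unsecured power statement, not a demonstrated lack of power.

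Separately, the 20% loss adjustment leaves 32 pairs and 79% power, one pair short of the stated 33.

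Severity is minor: quality of life is a secondary aim in a descriptive case series.

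**What to change.** In the Sample size section, the sponsor should state the number of participating endoscopists and whether 40 is a condition for closing or a target. The wording that 40 were required leaves that choice to the sponsor.

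- **If a target:** replace the unconditional 80% statement with power or detectable change over the plausible closing sizes for the actual number of endoscopists, using the 25-to-40 rows of the table in the working. Give the floor only as the worst case.
- **If a condition:** add it to the per-endoscopist condition in both the Sample size and Timeframe sections.
- **In either case:** enrol 42 for 33 pairs, or state 32 pairs and 79% power. In both sections, say which condition the 4-endoscopist qualifier governs, and use one threshold, either at least 5 or more than 5.

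The target route is text only; its price is a slightly less favourable power figure. The condition route costs recruitment. With 5 equal-volume endoscopists, the median size among closures below 40 is 34, so reaching 40 means about 6 more patients; from the floor with 4 endoscopists it means 20 more. Using 42 adds 2 to each. Recruitment is confined to years one and two, no accrual rate is given, and the plan itself notes the low volume ("Although EUS-GE is a rather infrequent procedure"). The delay therefore cannot be stated and might not fit.

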Categorical variables were reported as percentages. Normally distributed continuous variables were reported as the mean with the standard deviation values. Non-normally distributed continuous variables were reported as the median and interquartile range. The EORTC QLQ-C30 descriptive analysis was performed with a specifically programmed Stata command (10). Variables regarding the procedure step by step analysis will only undergo a descriptive analysis. Differences between the different outcomes of the EORTC-QLQ-C30 will be assessed using linear mixed models with fixed effects for baseline values, and interaction with oncological treatment. The statistical analysis will be performed using the Stata package (StataCorp. 2013, College Station, Texas).

7. Ethics

Benefit risk assessment

Patients taking part in the study will not gain any personal benefit. We consider taking part in the study does not increase the risks associated to the procedure. The study is purely observational; data retrieval will not be performed by the operator. Thus, we consider the procedure in participating patients should defer from those EUS-GE performed in other patients. Follow-up will be performed via telephone calls, so the patient will not have to travel to take part. The procedure associated risk are well documented in the published literature, with an adverse event risk of 5%. The main risk is a hollow viscus perforation, followed by GI bleeding, and sedation associated procedures (aspiration pneumonia).

The study product, AXIOS™ (Boston Scientific) 20x10mm and 15x10mm lumen apposing metal stents, was originally designed to create internal drains for pancreatic fluid collections. Currently they are used in various other indications. Their deployment creating EUS-GE in patients presenting malignant unresectable GOO is increasing, both in Europe and in the United States, with various published case series.

8. Timeframe

First year

Recruitment of patients. Follow-up

Second year

Recruitment of patients. Follow-up (Recruitment will be active until the predetermined sample size of a minimum of 5 procedures/endoscopist is reached or until a total sample size of 50 patients is reached, with at least 4 endoscopists including >5 procedures).

Third year

Data análisis. Presentation in scientific meetings. Manuscript redaction.

9. Bibliography

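### The loss allowance is miscalculated: 33 evaluable patients at 20% losses need 42 included, not 40, which leaves 32 (minor)

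*Combined protocol and SAP*

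**What the plan says.** Quality of life is a secondary aim in section 2 ("To assess the impact of the procedure on the quality of life of the participating patients"). It is the only endpoint with a power calculation, which is in section 5, Sample size, and opens "To assess the secondary endpoint of the quality of life". The inputs come from earlier publications that "reported mean global health status scores of 36.6 (SD: 20.1) and 45 (SD: 20.3) before treatment". The target is given as "To detect at least a 14-points change", "with a 5% alfa risk and an 80% power". The result is: "33 subjects were estimated to be needed. Assuming a 20% of losses, 40 patients were required".

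Recruitment is governed by a different rule in the same subsection: "recruitment will be active until a minimum of 5 procedures/endoscopist is reached or until a total sample size of 50 patients is reached". Section 8, Timeframe, repeats it ("until the predetermined sample size of a minimum of 5 procedures/endoscopist is reached"). Neither statement of the rule mentions 40.

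**The concern.** An allowance for losses should set the number included so that, after the assumed losses, the required number can still be analysed. The printed figures fail that test by subtraction alone: one fifth of 40 is 8, and 40 − 8 = 32, which is below 33. How 33 was obtained does not matter.

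At stake is whether the stated quality-of-life requirement delivers the evaluable number on which the plan rests its 80% power. The questionnaire is given at inclusion and at day 30, so I take an evaluable patient to be one with both assessments.

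**Working it through.** **Inputs (section 5, Sample size).** Evaluable patients needed: 33. Losses: 20%. Patients required: 40. Change to detect: 14 points. SDs before treatment: 20.1 and 20.3. Alpha 5%, power 80%. The document gives neither the sidedness of the test, nor an SD of the change, nor a correlation between inclusion and day 30.

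**Reproducing 33.** With a two-sided test and the normal formula n = 2 × SD² × (1.960 + 0.842)² / 14²:

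- SD 20.1: 32.36, rounded up to 33
- SD 20.2 (midpoint): 32.68, rounded up to 33
- SD 20.3: 33.005, rounded up to 34

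So 33 reproduces. The formula is the one for each of two independent groups, and equally the paired formula with zero correlation. A one-sided test would give 26.

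**Reproducing 40.** 33 × (1 + 0.20) = 39.6, rounded up to 40. This matches the printed figure, but the route is inferred.

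**Correct allowance.** n = 33 / (1 − 0.20) = 41.25, rounded up to 42.

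| Included | Left after 20% losses | At least 33? |
|---|---|---|
| 40 | 32.0 | no |
| 41 | 32.8 | no |
| 42 | 33.6 | yes |
| 50 | 40.0 | yes |

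With 40 included, losses can reach only (40 − 33)/40 = 17.5%. With 42 they can reach (42 − 33)/42 = 21.4%.

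**Effect on power.** If 33 gives exactly 80%, power at 32 is Φ((1.960 + 0.842) × √(32/33) − 1.960) = 78.8% by the normal approximation, or 78.7% for a paired t test, whatever the SD or correlation. If 33 was rounded up, power at 32 lies between that and 80%. With the plan's SDs in the formula above, 32 evaluable patients give 79.6% (SD 20.1), 79.2% (20.2) or 78.8% (20.3).

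**Against the stopping rule.** At 50 patients, 40 remain evaluable and power is about 87% by the same formula. The per-endoscopist branch fixes no total, because the number of endoscopists is not stated. For illustration only, eight endoscopists at the minimum give 8 × 5 = 40, short of 42, and nine give 9 × 5 = 45. Five is a floor, so actual totals could be higher.

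**Chance of reaching 33.** If each patient is lost independently with probability 0.20 (an assumption), the probability of at least 33 evaluable is 44% with 40 included, 68% with 42 and 99% with 50. So 42 meets the target in expectation, which is what a standard allowance does; it does not guarantee it.

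**The case against.** The strongest objection is that 40 follows a common shortcut, adding 20% of the evaluable number, and that on this reading nothing was miscalculated. That is the only reading that yields 40. It does not stand, because losses are taken from the patients included, and 20% of 40 leaves 32.

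A second objection is that 33 may not be the true threshold. The planned comparison is within patients, and any positive correlation between the two assessments lowers the need. At an assumed correlation of 0.05 and SD 20.3, the need is 33.005 × 0.95 = 31.4, and 32 evaluable patients give 80.8%. At 0.3 to 0.5 the need falls to about 17 to 24 (normal formula) or 19 to 26 (t-based). This part stands as a limit on the consequence: the loss of power is conditional on 33 being the right number. It does not make 33, 20% and 40 agree, and the document states no correlation to rely on.

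Third, the error changes nothing in the conduct of the study, since recruitment is not tied to 40, the primary aim is descriptive, and the 50-patient branch leaves ample numbers. This is right and is why the point is minor. The two recruitment conditions are alternatives, however, so 50 is not guaranteed, and 40 remains the only stated requirement for this endpoint.

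**Conclusion.** The concern holds, as a minor arithmetic error. Taking the plan's own 33 and 20% as given, the requirement is 42. The printed figure is two patients too low and leaves one evaluable patient too few. That conclusion needs no assumption about SD, correlation or sidedness.

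The power statement does rest on a condition: if 33 is the number that gives 80%, the shortfall costs at most about one percentage point. The design is not undermined, and the correction does not by itself alter how many patients are recruited.

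**What to change.** In section 5, Sample size, replace the final sentence of the quality-of-life calculation with: *Allowing for 20% losses, 33/(1 − 0.20) = 41.25, so 42 patients need to be included.* This is the better option because it depends only on figures already printed.

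Alternatively, keep 40 and say that 32 patients are then expected to be evaluable, with power slightly below 80% (about 79% if 33 is the number giving 80%). That wording depends on how 33 was derived, so the formula and SD used should be stated with it.

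The cost is one sentence. The figure of 42 is within the 50 patients already allowed, and the stopping rule in sections 5 and 8 can stay as it is.
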